#### Documented Hypoglycemia:

- **Documented symptomatic hypoglycemia:** An event during which typical symptoms of hypoglycemia are accompanied by plasma glucose (PG)  $\leq 70$  mg/dL ( $\leq 3.9$  mmol/L).
- **Documented asymptomatic hypoglycemia:** An event not accompanied by typical symptoms of hypoglycemia but with PG  $\leq 70$  mg/dL ( $\leq 3.9$  mmol/L).
- **Documented unspecified hypoglycemia:** An event during which PG  $\leq 70$  mg/dL ( $\leq 3.9$  mmol/L) but no information relative to symptoms of hypoglycemia was recorded.

**Probable symptomatic hypoglycemia:** An event during which symptoms typical of hypoglycemia are not accompanied by a PG determination but that was presumably caused by a PG concentration  $\leq 70$  mg/dL ( $\leq 3.9$  mmol/L).

**Relative hypoglycemia (also referred to as Pseudohypoglycemia):** An event during which the person with diabetes reports any of the typical symptoms of hypoglycemia with a measured PG concentration  $> 70$  mg/dL ( $> 3.9$  mmol/L) but approaching that level.

**Overall hypoglycemia:** This optional category combines all cases of hypoglycemia (documented hypoglycemia and probable symptomatic hypoglycemia, including severe hypoglycemia) excluding the events of relative hypoglycemia. Nocturnal and severe hypoglycemia are special cases of documented or probable hypoglycemia. If an event of hypoglycemia falls into multiple subcategories, that event should only be counted once in this category.

## 10. Efficacy, Health Outcome/Quality of Life Measures, Safety Evaluations, and Appropriateness of Measurements

Study procedures and their timing (including tolerance limits for timing) are summarized in the Study Schedule ([Attachment 1](#)).

### 10.1. Efficacy Measures

#### 10.1.1. Primary Measure

The primary efficacy measure is the change in HbA1c from baseline to 24 weeks.

#### 10.1.2. Secondary Efficacy Measures

The following measures will be considered for the comparison of other aspects of overall glycemic control:

- change in HbA1c from baseline to 4, 8, 12, 16, and 20 weeks or LOCF
- percentage of patients with HbA1c <7%; percentage of patients with HbA1c ≤6.5%
- 7-point SMBG measurements, as listed in the Study Schedule ([Attachment 1](#))
  - premeal for each meal
  - postmeal for each meal
  - bedtime
- inpatient variability, as measured by the standard deviation of the 7-point SMBG. Basal insulin dose (including U/day and U/kg/d)
- weight change
- patient-reported outcomes as reflected in responses to ITSQ

### 10.2. Health Outcome/Quality of Life Measures

Self-reported patient questionnaires will be utilized to compare health outcomes for the 2 insulins being studied. These health outcomes, specific to treatment satisfaction, will be reflected in responses to ITSQ administered at Visits 6, 12, Visit 18 and ED if a patient received at least one dose of study insulin.

The ITSQ is a validated instrument containing 22 items that assesses treatment satisfaction for persons with diabetes on insulin (Anderson et al. 2004). Items are measured on a 7-point scale, where lower scores reflect better outcomes. In addition to an overall score, the items that make up the 5 domains of satisfaction are categorized as:

- Inconvenience of Regimen (IR - 5 items)
- Lifestyle Flexibility (LF - 3 items)

- Glycemic Control (GC - 3 items)
- Hypoglycemic Control (HC - 5 items)
- Satisfaction with the Insulin Delivery Device (DD - 6 items)

All individual patient-domain scores will be calculated as the sum of the items in the domain. If item score is missing and less than 20% of the items within the domain are missing for that patient, then the mean of all other patients' scores for that item will be imputed for the item. Otherwise, the domain score will be missing for the patient.

### **10.3. Safety Evaluations**

Investigators are responsible for monitoring the safety of patients who have entered this study and alerting Lilly or its designee to any event that seems unusual, even if this event may be considered an unanticipated benefit to the patient.

The investigator is responsible for the appropriate medical care of patients during the study.

The investigator remains responsible for following, through an appropriate health care option, AEs that are serious (SAEs), considered related to the study treatment or the study, or that caused the patient to discontinue before completing the study. The patient should be followed until the event is resolved or explained. Frequency of follow-up evaluation is left to the discretion of the investigator.

#### **10.3.1. Adverse Events**

Lilly has standards for reporting AEs that are to be followed, regardless of applicable regulatory requirements that may be less stringent.

Lack of drug effect is not an AE in clinical studies because the purpose of the clinical study is to establish drug effect.

Study site personnel will record the occurrence and nature of each patient's preexisting conditions, including clinically significant signs and symptoms of the disease while under treatment in the study.

After the ICF is signed, site personnel will record any change in the condition(s) and the occurrence and nature of any AEs. All AEs related to protocol procedures are reported to Lilly or designee.

In addition, all AEs occurring after the patient receives the first dose of investigational product must be reported to Lilly or its designee via eCRF.

Any clinically significant findings from ECGs, labs, vital sign measurements, or other procedures that result in a diagnosis should be reported to Lilly or its designee.

Investigators will be instructed to report to Lilly or its designee their assessment of the potential relatedness of each AE to protocol procedure, studied disease state, investigational product, and/or drug delivery system via eCRF.

The investigator decides whether he or she interprets the observed AEs as either related to disease, to the study medication, study procedure, or other concomitant treatment or pathologies. To assess the relationship of the AE to the investigational product, the following terminologies are defined:

- **Related:** a direct cause and effect relationship between the study treatment and the AE is likely
- **Unrelated:** without question, the AE is definitely not associated with the study treatment

If a patient's dosage is reduced or treatment is discontinued as a result of an AE, study-site personnel must clearly report to Lilly or its designee via eCRF the circumstances and data leading to any such dosage reduction or discontinuation of treatment.

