Serious adverse events occurring up to and including the patient’s last visit will be collected, regardless of the investigator’s opinion of causation, in the clinical data collection database and the pharmacovigilance system at the sponsor.

Pregnancy (during maternal or paternal exposure to investigational product) does not meet the definition of an AE. However, to fulfill regulatory requirements any pregnancy should be reported following the SAE process to collect data on the outcome for both mother and fetus.

Investigators are not obligated to actively seek AEs or SAEs in subjects once they have discontinued and/or completed the study (the patient summary CRF has been completed). However, if the investigator learns of any SAE, including a death, at any time after a subject has been discharged from the study, and he/she considers the event reasonably possibly related to the study treatment or study participation, the investigator must promptly notify Lilly.

Information on SAEs expected in the study population independent of drug exposure and that will be assessed by the sponsor in aggregate periodically during the course of the trial may be found in the IB.

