#### **10.3.1.1.1. Suspected Unexpected Serious Adverse Reactions**

Suspected unexpected serious adverse reactions (SUSARs) are SAEs that are not listed in the IB and that the investigator identifies as related to investigational product or procedure. Lilly has procedures for the recording and expedited reporting of SUSARs that are consistent with global regulatory regulations and detailed guidances and will be followed.

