5.2.11. Safety Analyses

5.2.11.1. Adverse Events

Analyses of adverse events will include all data collected during the course of the entire study including the follow up visit, regardless of IP use.

Adverse events will be listed by patient, system organ class, Medical Dictionary for Regulatory Activities® (MedDRA) preferred term, severity, and relationship to the study disease, drug, device, or procedure for all patients. Adverse events (including injection site reactions, allergic events, and neoplasms) will be summarized as TEAEs for the FAS. Treatment-emergent adverse events are defined as events that are newly reported after first study treatment following randomization or reported to have worsened in severity from baseline. The proportion of patients experiencing each TEAE will be presented by preferred term, system organ class (SOC), and treatment group. The proportion of patients experiencing each TEAE that is assessed as possibly related to the study disease, drug, device, or procedures will also be summarized. The number of patients and proportion will be presented and compared by treatment using Fisher's

exact test or Pearson's chi-square test for the FAS population. TEAE will be summarized by preferred term within SOC and by preferred term by decreasing frequency.

All SAEs will be listed by patient and summarized by treatment as counts and percentages. If a sufficient number of SAEs are reported, the proportion of patients with SAEs between treatment groups will be compared using Fisher's exact test. Similar analyses will be performed for discontinuations due to AEs.

Summary table of historical conditions and pre-existing condition will be listed by preferred term and ordered by decreasing order of the total group. Historical conditions are conditions that end prior to inform consent and preexisting conditions are conditions that are still ongoing at inform consent or the conditions that started after inform consent and before first does.

A listing of subjects discontinue IP or study due to adverse event including death will be presented.

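### The protocol's two causality terms leave out events judged possible but not likely, yet the related-TEAE tables and the SUSAR definition depend on that call

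*Protocol*

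**What the plan says.** Protocol 10.3.1 asks investigators to report "their assessment of the potential relatedness of each AE to protocol procedure, studied disease state, investigational product, and/or drug delivery system via eCRF". It then introduces its definitions with "To assess the relationship of the AE to the investigational product, the following terminologies are defined" and gives two:

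- Related means that "a direct cause and effect relationship between the study treatment and the AE is likely".
- Unrelated sits at the other extreme and demands certainty that there is no link: "without question, the AE is definitely not associated with the study treatment".

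Neither document defines another causality term or says how to code an event that meets neither definition.

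Several later rules use the result:

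- **Safety tables.** SAP 5.2.11.1 states that the proportion of patients with each TEAE "assessed as possibly related to the study disease, drug, device, or procedures will also be summarized", and goes on to a between-arm test. Protocol 12.2.9.3 has the same provision.
- **SUSARs.** Protocol 10.3.1.1.1 defines these as "SAEs that are not listed in the IB and that the investigator identifies as related to investigational product or procedure". The entry in Section 4 has the same dependence.
- **Follow-up.** Protocol 10.3 lists events considered related to the treatment or the study among those the investigator must follow until they are resolved or explained.
- **Further analyses.** SAP 5.2.11.4 relates drug-related TEAEs to treatment-emergent antibody response (TEAR). SAP 5.2.12 analyses them by subgroup.

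For SAEs that come to light after discharge from the study, Protocol 10.3.1.1 uses another expression: the investigator notifies the sponsor if he or she "considers the event reasonably possibly related to the study treatment or study participation".

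**The concern.** A two-way causality scale works only if every event falls on one side. Here one term is set high (likely) and the other is set at certainty of no link, so the two do not meet. What lies between is a common clinical judgement: a link that cannot be ruled out but is not thought probable. That is also the group the safety tables say they will report.

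Two careful investigators could code the same event in opposite ways and each cite the protocol. The count of related TEAEs would then reflect site habit as well as the products. Whether an unexpected serious event meets the SUSAR definition would turn on the same unguided choice. For a non-serious event that does not lead to discontinuation, so would the duty to follow it to resolution. Investigators know the assignment (Protocol 9.7, SAP Section 6), so that choice could also be made differently in the two arms.

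**Working it through.** No figure in the plan bears on this point, so the check is a comparison of texts.

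**Step 1: do the two definitions cover every judgement?**

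| Investigator's judgement | Meets Related (10.3.1)? | Meets Unrelated (10.3.1)? | Belongs in a *possibly related* table? |
|---|---|---|---|
| Direct causation likely | Yes | No | Yes |
| Possible, not likely | No | No | Yes |
| Unlikely, not excluded | No | No | Not stated |
| Excluded with certainty | No | Yes | No |

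The two middle rows have no code. The second row falls squarely within what Protocol 12.2.9.3 and SAP 5.2.11.1 say will be summarised.

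**Step 2: is there a default or a mapping?** I found none in either document. One could argue that anything short of certain exclusion should be Related, and the request for *potential* relatedness leans that way. The condition that causation be likely contradicts it. The SAP does not say which recorded response feeds the *possibly related* tables, nor whether its *related to study drug* analyses use the same set.

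**Step 3: do the definitions cover the relationships that are tabulated?** They address the investigational product only. Relatedness to procedure, disease and delivery system is also collected (10.3.1). Relatedness to disease, device and procedure is also summarised (12.2.9.3, SAP 5.2.11.1). The SUSAR definition includes relatedness to procedure. No terms are defined for these relationships.

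**Step 4: what uses the call, and what does not?**

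- Uses it: the SUSAR definition (Protocol Section 4 and 10.3.1.1.1), follow-up of related events (10.3), related-TEAE tables (12.2.9.3, SAP 5.2.11.1), TEAR by adverse-event category (SAP 5.2.11.4), and subgroup analyses of drug-related TEAEs (SAP 5.2.12).
- Does not use it: the HbA1c analyses, the overall TEAE and SAE tables, discontinuations due to adverse events, allergic events (found by blinded review of preferred terms, SAP 5.2.11.1.1), injection-site events and hypoglycemia.

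**The case against.** The strongest reply is that little follows in practice, and much of it stands.

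- **Escape from SUSAR handling.** A reader might infer that an uncertain serious event will be entered as Unrelated and lost to expedited reporting. The documents do not support this. Taken literally, Unrelated demands certainty, so an uncertain event cannot properly be entered there. After first dose, sites must alert the sponsor to any SAE within 24 hours. SAEs up to the last visit enter the clinical database and the sponsor's pharmacovigilance system whatever the investigator thinks of causation (10.3.1.1). The sponsor reviews SAEs (10.3.3), and its SUSAR procedures, which are not in the documents, may add safeguards. Still, receiving an event is not the same as classifying it, and the written SUSAR definition turns on the investigator's call.
- **Bias between arms.** A reader might infer a bias for or against the new product. Nothing shows that coding will differ or in which direction, and unblinded causality judgements stay subjective under any wording. What stands is that undefined middle ground leaves more room for such a difference.
- **The form.** A reader might infer that the eCRF lacks a category. The eCRF and its completion guidance are not available, so the point concerns the protocol's definitions only.
- **Competing thresholds.** The post-discharge expression in 10.3.1.1 triggers a separate notification duty. It is not a coded response, so its difference from 10.3.1 is not itself a contradiction.
- **Obvious mapping.** With two terms, counting Related as *possibly related* is the natural choice. That settles which code is tabulated, but not how a possible event gets its code.

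**Conclusion.** The definitions in Protocol 10.3.1 are not exhaustive, and the events they omit include those the protocol and SAP undertake to tabulate. This is a fault in a stated rule: a site that follows it exactly cannot code a possible-but-not-likely event, and sites that improvise may do so differently. The related-TEAE tables, the analyses built on them and the SUSAR classification are unreliable to that extent.

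The size cannot be estimated, because the documents give neither the expected number of such events nor a split by judgement. The effect is confined to outputs that use the causality call. The primary noninferiority conclusion and the overall safety tables are untouched.

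The conclusion assumes that no completion guidance outside these documents supplies a default. If such guidance exists, citing it in the protocol and SAP would meet most of the point.

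**What to change.** 1. In Protocol 10.3.1, make the categories complementary. Related: there is a reasonable possibility that the study treatment caused the event. Unrelated: there is no reasonable possibility.
2. Apply the same pair to procedure, disease and device, since these relationships are also recorded and summarised.
3. Use the same term in Protocol Section 4 (SUSAR entry), 10.3.1.1, 10.3.1.1.1 and 12.2.9.3, and in SAP 5.2.11.1.
4. State in the SAP that Related is the response counted in both the *possibly related* and the *related to study drug* tables, including those in 5.2.11.4 and 5.2.12.

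The cost is wording in the protocol, the SAP and any eCRF guidance, plus a note to sites. The downside is that somewhat more events may be classed as related. If events have already been coded under the present wording, the sponsor should also decide whether sites review those codes, so that one table does not mix two definitions.

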#### **10.3.1.1. Serious Adverse Events**

Serious adverse event collection begins after the patient has signed informed consent and has received investigational product. If a patient experiences an SAE after signing informed consent, but prior to receiving investigational product, the event will NOT be reported as serious unless the investigator feels the event may have been caused by a protocol procedure.

Planned surgeries should not be reported as SAEs unless the underlying medical condition has worsened during the course of the study.

Study site personnel must alert Lilly or its designee via a sponsor-approved method of any SAE within 24 hours of investigator awareness of the event via a sponsor-approved method. If alerts issued via telephone, they are to be immediately followed with official notification on study-specific SAE forms. This 24-hour notification requirement refers to the initial SAE information and all follow-up SAE information.

An SAE is any AE from this study that results in one of the following outcomes:

- death
- initial or prolonged inpatient hospitalization
- a life-threatening experience (that is, immediate risk of dying)
- persistent or significant disability/incapacity
- congenital anomaly/birth defect
- that which is considered significant by the investigator for any other reason

Important medical events that may not result in death, be life-threatening, or require hospitalization may be considered an SAE when, based upon appropriate medical judgment, they may jeopardize the patient and may require medical or surgical intervention to prevent one of the outcomes listed in this definition.

**For the purposes of this protocol, all episodes of severe hypoglycemia will be considered an SAE.** If the investigator believes that a reported SAE of hypoglycemia does not meet any of the specific criteria outlined above (that is, death, initial or prolonged inpatient hospitalization, a life-threatening experience, persistent or significant disability/ incapacity, or congenital anomaly/birth defect), the outcome of “considered significant by the investigator for any other reason” should be selected in the eCRF.

When a condition related to LY2963016 or Lantus® necessitates medical or surgical intervention to preclude either permanent impairment of a body function or permanent damage to a body structure, the serious outcome of “required intervention” will be assigned.

Serious adverse events occurring up to and including the patient’s last visit will be collected, regardless of the investigator’s opinion of causation, in the clinical data collection database and the pharmacovigilance system at the sponsor.

Pregnancy (during maternal or paternal exposure to investigational product) does not meet the definition of an AE. However, to fulfill regulatory requirements any pregnancy should be reported following the SAE process to collect data on the outcome for both mother and fetus.

Investigators are not obligated to actively seek AEs or SAEs in subjects once they have discontinued and/or completed the study (the patient summary CRF has been completed). However, if the investigator learns of any SAE, including a death, at any time after a subject has been discharged from the study, and he/she considers the event reasonably possibly related to the study treatment or study participation, the investigator must promptly notify Lilly.

Information on SAEs expected in the study population independent of drug exposure and that will be assessed by the sponsor in aggregate periodically during the course of the trial may be found in the IB.

#### **10.3.1.1.1. Suspected Unexpected Serious Adverse Reactions**

Suspected unexpected serious adverse reactions (SUSARs) are SAEs that are not listed in the IB and that the investigator identifies as related to investigational product or procedure. Lilly has procedures for the recording and expedited reporting of SUSARs that are consistent with global regulatory regulations and detailed guidances and will be followed.

#### **10.3.2. Other Safety Measures**

Hypoglycemic events, vital signs, and weight will be collected as indicated in the Study Schedule ([Attachment 1](#)). Twelve-lead ECGs will be collected locally according to the Study Schedule ([Attachment 1](#)).

The ECG will be interpreted by a qualified physician (the investigator or qualified designee) at the site as soon after the time of ECG collection as possible, and ideally while the patient is still present, for immediate patient management and to determine whether the patient meets entry criteria.

### **10.3.3. Safety Monitoring**

The Lilly CRP or medical designee will monitor safety data throughout the course of the study.

Lilly will review SAEs within time frames mandated by company procedures. The Lilly CRP or medical designee will, as is appropriate, consult with the functionally independent GPS therapeutic area physician or clinical scientist, and periodically review:

- trends in safety data
- laboratory analytes
- adverse events

If a study patient experiences elevated ALT or AST  $\geq 3X$  ULN or elevated total bilirubin  $\geq 2X$  ULN, clinical and laboratory monitoring should be initiated by the investigator. Details for hepatic monitoring depend upon the severity and persistence of observed laboratory test abnormalities. To ensure patient safety and comply with regulatory guidance, the investigator is to consult with the Lilly designated medical monitor regarding collection of specific recommended clinical information and follow-up laboratory tests. See [Attachment 2](#) and [Attachment 4](#).

